## 11.4. Determination of sample size

The sample size determination enables the evaluation of the non-inferiority of HZ recurrence incidence rate, and to rule out a 5-fold increased risk of HZ recurrence in the HZ/su group compared to the placebo group. The following assumptions were made:

- Incidence rate of HZ recurrence in the placebo group= 0.55% per year.
- Incidence rate of HZ recurrence in the HZ/su group= 0.275% per year, assuming a 50% vaccine efficacy.
- Power of 90% and Type I error of 0.025 (one-sided).
- Criterion for non-inferiority = 5-fold; the 5-fold criterion has been selected as acceptable for ruling out a moderate increased risk of HZ in a clinical trial setting.

Let  $\pi$  be the ratio of incidence rate of HZ recurrence in HZ/su group vs the placebo group, then null hypothesis  $H_0: \pi \geq 5$  vs. alternative hypothesis  $H_a: \pi < 5$ . With the assumption that the number of HZ recurrence cases in HZ/su and placebo group follows Poisson distribution independently, conditioning on the total number of cases, the number of cases in HZ/su group would follow the binomial distribution [Lehmann, 1959]. With 1:1 randomization, the parameter  $p$  in the binomial distribution (that is, the probability of HZ recurrence in HZ/su group) is expected to be  $p=\pi/(1+\pi)$ . Therefore, the above hypotheses becomes:  $H_0: p \geq 0.8333$  vs.  $H_a: p < 0.8333$ . Under the assumption of VE of 50%, a total number of 10 HZ recurrence cases is needed (PASS 12: Tests for One Proportion using proportions (Exact Test)). With incidence rate of 0.55% per year and two year follow up, 606 evaluable subjects per group are needed. Further assuming a dropout rate of 15% during the 2 year follow up period, 713 subjects per group (a total of 1426 subjects) need to be enrolled.

CCI

A large black rectangular redaction box covers the majority of the page content below the CCI label, starting from the bottom of the CCI label and extending down to just above the section 11.4.2 header.

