### 3. STUDY DESIGN OVERVIEW

**Figure 1 Overview of Study Design**

BS= Blood sampling; HZ= Herpes Zoster; N= number of subjects planned to be enrolled; Vacc= Vaccination

\*A blood sample (approx. 5ml per visit) will be collected from all subjects at Visits 1, 2 and 3. CCI [REDACTED]

‡ The duration of the study will vary for each subject. Study conclusion will be scheduled based on the projected date of the last contact of the last enrolled subject, that is 26 months (790 days) from the enrolment date. The study conclusion visit/ contact for subjects with an ongoing episode of HZ will occur after a 4-week pain-free period is documented OR after Day HZ-92 follow-up has been completed.

Protocol waivers or exemptions are not allowed unless necessary for the management of immediate safety concerns. Therefore, adherence to the study design requirements, including those specified in the outline of study procedures (Section 6.5), are essential and required for study conduct. **Refer to Section 6.7 for study procedures to be considered during special circumstances (Amended 14 April 2020).**

- **Experimental design:** Phase III, observer-blind, randomized, placebo controlled, multicenter, multi-country study with two parallel groups.
- **Duration of the study:** The duration of the study will vary for each subject. The duration of the study will be up to the study conclusion contact that occurs within 30 days of the projected study conclusion date of the last enrolled subject, that is, 26 months (790 days) from the enrolment date. Therefore subjects enrolled early in the trial could be followed for longer duration than the subjects who enrol later in the trial. The study conclusion visit/ contact for subjects with an ongoing episode of HZ at the time of LSLV will occur after a 4-week pain-free period is documented OR after Day HZ-92 follow-up has been completed.
  - **Epoch 001:** Starting at Visit 1 (Day 1) followed by Visit 2 at two months post first vaccination (Month 2), Visit 3 at one month post last vaccination (Month 3).
  - **Epoch-002:** Starting with monthly contact after Visit 3 (Month 3) and ending at the monthly contact that occurs within 30 days of the projected study conclusion date of the last enrolled subject, that is, 26 months (790 days) from the enrolment date.

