### **5.3. Exclusion criteria for enrolment**

Deviations from exclusion criteria are not allowed because they can potentially jeopardize the scientific integrity regulatory acceptability of the study, or subject safety. Therefore, adherence to the criteria as specified in the protocol is essential.

The following criteria should be checked at the time of study entry. If ANY exclusion criterion applies, the subject must not be included in the study:

- Subjects who at time of study entry or during the maximum period of anticipated study participation (approximately 4 years) are/will become part of the population recommended to receive a zoster vaccine per existing local or national immunization practices will be excluded from study participation.
- Use of any investigational or non-registered product (drug or vaccine) other than the study vaccine during the period starting 30 days before the first dose of study vaccine (Day -30 to Day 1), or planned use during the study period.
- Any medical condition that in the judgment of the investigator would make intramuscular injection unsafe.
- Onset of HZ in the past 6 months or any ongoing symptoms from a prior HZ episode.
- Chronic antiviral use for HZ prophylaxis.
- History of > 1 prior episode of HZ.

- A history of disseminated HZ, cutaneous or associated with visceral disease (defined as an abnormality of one or more internal organs [e.g., hepatitis, pneumonitis, gastroenteritis, etc] caused by VZV infection) or associated with neurologic disease (defined as cranial or peripheral nerve palsies, myelitis, meningoencephalitis or stroke) caused by VZV infection.
- Use or anticipated use of immunosuppressants or immune-modifying drugs during the period starting six months prior to study start and during the whole study period. This includes chronic administration of corticosteroids (> 14 consecutive days of prednisone at a dose of  $\geq$  20 mg/day [or equivalent]) (intra-articular, inhaled and topical steroids are allowed), long-acting immune-modifying agents (e.g., infliximab) or immunosuppressive/cytotoxic therapy (e.g., medications used during cancer chemotherapy, organ transplantation or to treat autoimmune disorders).

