### **6.6.16. Study conclusion**

Study conclusion will be scheduled based on the projected date of the last contact of the last enrolled subject, that is, 26 months (790 days) from the enrolment date. All sites will be notified of this date as to schedule the study conclusion contact for all subjects within 30 days of that date.

The study conclusion visit/ contact for subjects with an ongoing episode of HZ will occur after a 4-week pain-free period is documented OR after Day HZ-92 follow-up has been completed (see [Table 8](#)).

At the study conclusion contact the investigator will:

- review data collected to ensure accuracy and completeness,
- complete the Study Conclusion screen in the eCRF.

After study conclusion, placebo recipients may be offered cross-over vaccination with HZ/su, if supported by study results.

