## 11. STATISTICAL METHODS

### 11.1. Primary endpoint

Occurrence of confirmed HZ episodes from 30 days post second vaccination until study end.

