### 11.11.2. Sequence of analyses

There will be only one final analysis following end of the study.

A clinical study report containing all data will be written and made available to the investigators.

If the data for tertiary endpoints become available at a later stage, (an) additional analysis/ analyses will be performed. These data will be documented in annex(es) to the study report.

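### The 90% power in Protocol 11.4 holds only if at least 10 cases accrue; on the section's own inputs, power averaged over the random case count is about 85.5%

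*Protocol*

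**What the plan says.** Protocol section 11.4 lists "Power of 90% and Type I error of 0.025 (one-sided") among its assumptions, with a recurrence rate of 0.55% per year on placebo, 0.275% per year on HZ/su (50% efficacy) and a rate-ratio margin of 5. It treats the two case counts as independent Poisson variables, conditions on their total, and concludes from an exact one-proportion test that "a total number of 10 HZ recurrence cases is needed". It then states: "With incidence rate of 0.55% per year and two year follow up, 606 evaluable subjects per group are needed". A 15% dropout allowance brings this to 713 per group.

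Elsewhere the protocol fixes when the trial ends. Section 6.6.16: "Study conclusion will be scheduled based on the projected date of the last contact of the last enrolled subject". That contact falls 790 days after the last subject's enrolment. Section 11.11.2: "There will be only one final analysis following end of the study". Section 11.11.3 plans no interim analysis. I found no minimum number of cases required before the analysis.

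Three further passages affect person-time:
- Section 11.1 defines the endpoint as "Occurrence of confirmed HZ episodes from 30 days post second vaccination until study end", so the at-risk clock starts about 90 days after enrolment.
- Section 3 notes: "Therefore subjects enrolled early in the trial could be followed for longer duration than the subjects who enrol later in the trial".
- Protocol 10.2.1 and SAP 9.1.3 count dropouts up to their last contact.

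**The concern.** Section 11.4 moves from a fixed-total calculation (10 cases give at least 90% power) to a sample size under which 10 is only the mean. In an event-driven trial the two agree, because follow-up continues until the cases occur. Here follow-up stops on a date, so the total is random under the section's own Poisson model, and the section does not average over it.

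The loss is not symmetric. Counts above 10 have little power left to gain, while counts below 10 lose a good deal. A reader who takes 90% as the chance of meeting the primary objective at 50% efficacy would be taking too high a figure. This matters for interpretation: virus reactivation in people with prior HZ is listed in section 1.3.1 as a potential risk added at the request of EU authorities. If non-inferiority were missed, the prior chance of that result under a truly effective vaccine would be needed to read it.

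**Working it through.** **Inputs.** From Protocol 11.4: rates 0.0055 and 0.00275 per year, margin 5, one-sided 0.025, 606 evaluable per group, 2 years. From 11.8: success if the upper limit of the 95% Clopper-Pearson-based interval is below 5. With equal person-time, the case share on HZ/su is p = 5/6 at the margin and p = 0.5/1.5 = 1/3 at 50% efficacy.

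**Step 1: reproduce the plan's figures.** Let c(n) be the largest HZ/su count out of n total cases whose upper limit for p is below 5/6. Conditional power is P(X ≤ c(n)) for X ~ Binomial(n, 1/3).

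| Total cases n | c(n) | Conditional power |
|---|---|---|
| 2 or fewer | none | 0 |
| 3 | 0 | 29.6% |
| 4 | 1 | 59.3% |
| 5 | 1 | 46.1% |
| 6 | 2 | 68.0% |
| 7 | 3 | 82.7% |
| 8 | 3 | 74.1% |
| 9 | 4 | 85.5% |
| 10 | 5 | 92.3% |
| 11 | 6 | 96.1% |
| 12 | 6 | 93.4% |

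Ten is the smallest total reaching 90%, and no total from 10 to 79 falls below 92.3%. Subjects per group: 10 / [2 × (0.0055 + 0.00275)] = 10 / 0.0165 = 606. Enrolled: 606 / 0.85 = 712.9, so 713. All three planned numbers reproduce.

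**Step 2: average over the random total.** Expected cases: μ = 606 × 2 × 0.00825 = 10.0. Power = Σ Poisson(n; μ) × P(X ≤ c(n) | n, 1/3).

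- P(fewer than 10 cases) = 45.8%; average power within that set is 74.0%.
- P(10 or more) = 54.2%; average power within that set is 95.3%.
- Overall: 0.458 × 0.740 + 0.542 × 0.953 = 0.855.

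One million simulated trials gave 85.6%. Binomial rather than Poisson arms gave 85.7%.

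**Step 3: what 90% requires.** Solving for power = 0.90 gives μ = 11.40, or 11.40 / 0.00825 ≈ 1,381 at-risk person-years per group. That is a mean of 2.28 years over 606 subjects, or 1.94 years over all 713.

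**Step 4: sensitivity to person-time.** The documents give no accrual curve or dropout timing. The following are therefore assumptions: uniform accrual (adding half the accrual period to mean follow-up), dropouts contributing half the period, and everyone qualifying for the modified Exposed Set. The 700 days are 790 − 90.

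| Scenario, per group | Person-years | Expected cases | Power | P(fewer than 10) |
|---|---|---|---|---|
| 606 × 2.0 years (as in 11.4) | 1,212 | 10.00 | 85.5% | 46% |
| 606 × 700 days | 1,161 | 9.58 | 83.9% | 51% |
| 606 × 2.0 years, plus 107 dropouts at half | 1,319 | 10.88 | 88.5% | 35% |
| 606 × 700 days, plus 107 dropouts at half | 1,264 | 10.43 | 87.1% | 41% |
| 606 × 700 days, plus 12 months' accrual | 1,464 | 12.08 | 91.7% | 24% |
| 606 × 700 days, plus 22 months' accrual | 1,717 | 14.16 | 95.3% | 10% |

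On the 700-day basis, 90% is reached with about 8.7 months of accrual without dropout time, or about 4.3 months with it. The 22 months come from Protocol 5.3, which refers to enrolment status "during the maximum period of anticipated study participation (approximately 4 years"): 48 − 26 = 22.

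**The case against.** The strongest reply is that nothing in 11.4 is miscalculated. The 10, the 606 and the 713 are correct, the section says openly that it conditions on the total, and setting the expected count equal to the required count is a common planning shortcut. All of that stands. But the section also states 90% as the power of the design, without qualification, and a design that only expects 10 cases does not have it.

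The second reply is that 85.5% describes a simplification. Section 11.4 gives dropouts no person-time and stops everyone at two years, whereas the trial follows early enrollees longer and counts dropouts to last contact. The roughly four-year maximum participation suggests about 22 months of accrual and power near 95%, or 96.6% with half-period dropout time added. The COVID-19 enrolment gap acknowledged in SAP 5.3.2 lengthens follow-up further for those enrolled before it. This has real force: the trial may well exceed 90%.

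Some features work the other way. Risk time starts 30 days after dose 2, and Protocol Table 11 allows dose 2 up to 180 days after dose 1. The 83.9% scenario is close to a floor, since Table 9 gives the last subject 730 to 760 days from Visit 2, or 700 to 730 days at risk. None of these effects, in either direction, enters the readable text of 11.4.

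**Conclusion.** The concern holds. On the inputs in section 11.4, unconditional power at 50% efficacy is 85.5%, about 4.5 points below the stated 90%. The chance of missing the objective is 14.5% rather than 10%. This rests on Poisson counts, equal person-time in the groups, the stated rates and exactly 1,212 person-years per group.

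It is not a forecast of the trial's power. Across the assumed scenarios above, that runs from 83.9% to 95.3%, and what decides it is accrual length and dropout person-time. The defect is that the plan's 90% is not derived from the plan's inputs, not that the trial is shown to be too small. The validity of the test is not in question.

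**What to change.** Restate 11.4 along these lines: *Power is 92% if exactly 10 cases accrue. Averaged over a Poisson count with mean 10 (606 per group × 2.0 years = 1,212 at-risk person-years per group), it is about 86%. Power of 90% requires about 11.4 expected cases, or about 1,380 at-risk person-years per group counted from 30 days after dose 2.* Then state the expected accrual period and mean at-risk follow-up, including time from early enrollees and dropouts, and give the unconditional power that results.

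The cost is a few sentences and a projection of person-time. The restatement itself calls for no extra enrolment. The published power figure may fall, or stay at 90% or more if expected person-time reaches about 1,380 years per group.

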### 11.4.2. Time since previous HZ sub-groups and age category

- To allow a descriptive analysis of the results the target will be to enrol a minimum of:
- 143 subjects in each ( $\leq 4$  years ago, 5-9 years ago,  $\geq 10$  years ago) “time since previous HZ episode” category.

- 285 subjects in 50-59 and 60-69 YOA category and 143 subjects in  $\geq 70$  YOA category.

## 11.5. Cohorts for Analyses

### 11.5.1. Exposed Set

The exposed set (ES) will include all vaccinated subjects with at least one study vaccine administered.

The ES for analysis of immunogenicity will include all vaccinated subjects for whom data related to immunogenicity endpoints are available.

The ES for analysis of reactogenicity will include all subjects with at least one vaccine administration documented.

#### 11.5.1.1. Modified Exposed Set

The modified exposed set (mES) is the primary population for HZ recurrence analysis. The mES excludes subjects in the ES who were not administered the second dose of the study vaccine or who developed a confirmed case of HZ prior to 30 days after the second vaccination.

### 11.5.2. Per Protocol Set for immunogenicity

The per protocol set (PPS) for immunogenicity will be defined by time-point (Month 2 and Month 3) and will include evaluable subjects from the ES:

- who meet all eligibility criteria.
- who received 2 doses of the HZ/su study vaccine or placebo according to their random assignment.
- who did not receive forbidden medications as defined in the protocol.
- who had no IMC which may influence immune response.
- who complied with the vaccination schedule as specified in [Table 9](#).
- who complied with the blood sample schedule as specified in [Table 9](#).
- for whom data concerning immunogenicity endpoint measures are available.

## 11.6. Derived and transformed data

### 11.6.1. Handling of missing data

For the analysis of solicited AEs, missing or non-evaluable measurements will not be replaced. Therefore, the analysis of the solicited AEs based on the ES will include only subjects/doses with documented safety data (that is symptom screen/sheet completed).

For the analysis of HZ recurrence/unsolicited AEs/SAEs/pIMDs/concomitant medication, all vaccinated subjects will be considered and subjects who did not report an event will be considered as subjects without an event.

For a given subject and a given immunogenicity measurement, missing or non-evaluable measurements will not be replaced. Therefore, an analysis will exclude subjects with missing or non-evaluable measurements.

## 11.7. Analysis of demographics

Demographic characteristics (age at first study vaccination in years, gender and ethnicity), 'time since previous HZ episode', age stratum and withdrawal status will be summarized by group using descriptive statistics:

- Frequency tables will be generated for categorical variable such as age stratum, 'time from previous HZ episode' and gender.
- Mean, median, Standard Deviation (SD) will be provided for continuous data such as age.
- The analysis will be based on ES.

## 11.8. Analysis of incidence rate of Herpes Zoster recurrence

For each group, the number of subjects, person-time, number of confirmed HZ cases and incidence rate will be tabulated.

A formal non-inferiority analysis with a non-inferiority margin of 5 will be performed in the final analysis. Non-inferiority assessment will be carried out based on the fact that the distribution of two Poisson variates conditional on their sum is binomial [Lehmann, 1959]. Let  $n_1$  and  $n_0$  be the number of HZ recurrence cases,  $T_1$  and  $T_0$  (years) be total follow up, and  $r_1$  and  $r_0$  be the incidence rate in HZ/su group and placebo group respectively. It is assumed that  $n_i \sim \text{Poisson}(\lambda_i)$  ( $i=0,1$ ) and  $\lambda_i = T_i \times r_i$ , and condition on  $n = n_0 + n_1$ ,  $n_1 \sim \text{binomial}(n, p)$ , where  $p = \lambda_1 / (\lambda_1 + \lambda_0)$ . A 95% exact CI for  $p$  can be derived by using Clopper-Pearson approach, through which a 95% exact CI for  $\pi = r_1 / r_0$  (that is, the ratio of incidence rate of HZ recurrence (HZ/su versus placebo)) can be derived. Non-inferiority is met if the upper limit of the 95% CI for  $\pi$  is below 5.

In addition to performing a formal non-inferiority analysis, to further quantify the likelihood of the risk increase of HZ following Shingrix vaccination, a probability curve that the ratio of incidence of HZ recurrence (HZ/su versus placebo) is higher than  $x$ -fold ( $x$  varying from 1 to 5) will be estimated by Bayesian methodology. It will be assumed that the number of HZ cases in the HZ/su and in placebo groups follows Poisson distribution with rate (incidence rate) of  $\lambda_{HZ}$  and  $\lambda_p$  respectively. We further assume that  $\lambda_{HZ}$  and  $\lambda_p$  are random variables both with non-informative Gamma prior distribution:  $\text{Gamma}(0.001, 0.001)$ . Based on the posterior distribution of  $\lambda_{HZ}$  and  $\lambda_p$ , the probability curve of the ratio of incidence of HZ recurrence (HZ/su versus placebo), that is,  $\text{Pr}(\lambda_{HZ}/\lambda_p > x | \text{data, prior})$ , can be calculated for each given value of  $x$ . This will be further detailed in the statistical analysis plan (SAP).

The primary analysis of incidence rate of HZ recurrence will be based on the mES. The analysis will be repeated for the ES.

## 11.9. Analysis of immunogenicity

The primary analysis will be based on the PPS for analysis of immunogenicity. If, in any group, the percentage of vaccinated subjects with serological results excluded from the PPS for analysis of immunogenicity is 5% or more, a second analysis based on the ES will be performed to complement the PPS analysis.

### 11.9.1. Humoral immune response

A seronegative subject is a subject whose Ab concentration is below the cut-off value.

A seropositive subject is a subject whose Ab concentration is greater than or equal to the cut-off value.

The seropositivity rate is defined as the percentage of seropositive subjects.

The vaccine response rate (VRR) for anti-gE is defined as the percentage of subjects who have at least:

- a 4-fold increase in the post last vaccination anti-gE Ab concentration as compared to the pre-vaccination anti-gE Ab concentration, for subjects who are seropositive at baseline, or,
- a 4-fold increase in the post last vaccination anti-gE Ab concentration as compared to the anti-gE Ab cut-off value for seropositivity, for subjects who are seronegative at baseline.

The geometric mean concentration (GMC) calculations are performed by taking the anti-log of the mean of the log concentration transformations. For descriptive statistics only, Ab concentrations below the cut-off of the assay will be given an arbitrary value equal to half the cut-off for the purpose of GMC calculation.

### Within groups assessment

[figure not shown]
The following descriptive analyses will be performed for each group and by age stratum (50-59 YOA; 60-69 YOA and  $\geq$ 70 YOA) and by 'time since previous HZ episode' ( $\leq$ 4 years ago, 5-9 years ago,  $\geq$ 10 years ago):

- Seropositivity rate at Day 1, Month 2 and Month 3 with exact 95% CI
- GMC at Day 1, Month 2 and Month 3 with 95% CI
- VRR at Month 2 and Month 3 with exact 95% CI
- Descriptive statistics of the fold over pre-vaccination at Month 2 and Month 3 (Mean, SD, Min, Q1, Median, Q3, Max).

**CONFIDENTIAL**

204939 (ZOSTER-062)  
Protocol Amendment 2 Final

CCI

## 11.10. Analysis of safety

[figure not shown]
The analysis will be performed on the ES. When appropriate, tabulations will be presented overall and by time of occurrence relative to last vaccination (e.g., using windows such as Days 1-7, Days 1-30 and more than 30 days post-vaccination). Safety analyses will also be performed by age stratum (50-59 YOA; 60-69 YOA and  $\geq 70$  YOA) and by 'time since previous HZ episode' ( $\leq 4$  years ago, 5-9 years ago,  $\geq 10$  years ago).

The results for the analysis of safety will be tabulated as:

- The proportion of subjects with at least one local AE (solicited or unsolicited), with at least one general AE (solicited or unsolicited) and with any AE (solicited or unsolicited) during the solicited 7-day follow-up period will be tabulated with exact 95% CI after each vaccine dose and overall.
- The proportion of subjects with at least one local AE (solicited only), with at least one general AE (solicited only) and with any AE (solicited only) during the solicited 7-day follow-up period will be tabulated with exact 95% CI after each vaccine dose and overall.
- The proportion of subjects reporting each individual solicited local and general AE during the solicited 7-day-follow-up period will be tabulated with exact 95% CI.
- For all solicited AEs, the same tabulation will be performed for grade 3 solicited AEs and for solicited general AEs with relationship to vaccination
- The proportion of solicited AEs resulting in a medically attended visit will be tabulated.
- Total duration of each individual solicited local and general AE will be tabulated.
- The proportion of subjects reporting temperature by half degree ( $^{\circ}\text{C}$ ) cumulative increments. Similar tabulations will be performed for any fever with a causal relationship to vaccination and for any fever resulting in a medically attended visit.
- The proportion of subjects with at least one report of unsolicited AE classified by the MedDRA system organ class (SOC) and preferred term (PT) and reported up to 30 days after each vaccination will be tabulated with exact 95% CI.
- The same tabulation will be performed for grade 3 unsolicited AEs and for unsolicited AEs with a relationship to vaccination. The proportion of AEs resulting in a medically attended visit will also be tabulated.
- Total number/percentages of doses (per dose and overall) followed by AEs will be tabulated.
- All pIMDs and related pIMDs occurring from first vaccination up to 30 days post last vaccination will be tabulated.
- All pIMDs and related pIMDs occurring after 30 days post last vaccination until 1 year post last vaccination will be tabulated.
- All SAEs, related SAEs occurring from first vaccination up to 30 days post last vaccination will be tabulated.

- All SAEs, related SAEs occurring after 30 days post last vaccination until one year post last vaccination will be tabulated.
- Fatal SAEs will be tabulated using date of onset of SAE in the following manner – within Day 1-Month 3 (30 days post last vaccination), Day 1 to Month 14 (one year post last vaccination) and Month 3 till study end. Fatal SAEs will also be tabulated using the date of death within the same time periods.
- All SAE related to investigational vaccine, related to study participation or to GSK concomitant medication/vaccine occurring during the entire study period will be tabulated.
- AEs/SAEs leading to withdrawal from the study will be tabulated.

CCI

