### 9.3.3.4. Medically attended visits

For each solicited and unsolicited AE/SAE the subject experiences, the subject/subject's LAR/caregiver will be asked if he/she /the subject received medical attention defined as hospitalization, or an otherwise unscheduled visit *by* medical personnel for any reason, including emergency room visits. This information will be recorded in the eCRF *(Amended 14 April 2020)*.

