9.1.4. Safety

- For the analysis of **CCI** /HZ related complications/solicited AEs/unsolicited AEs/SAEs/pIMDs/ concomitant medication, all vaccinated subjects will be considered and subjects who did not report an event will be considered as subjects without an event.
- AEs that need to be reported as pIMDs are listed in Table 20 of the protocol.
- The maximum intensity of local injection site redness/swelling will be graded as:

[figure not shown]
0	<20 mm diameter
1	≥20 mm to – ≤50 mm diameter
2	>50 mm to – ≤ 100 mm diameter
3	>100 mm diameter

- The fever grading to be considered for analysis will be:

0	<38.0°C
1	≥38.0°C – ≤38.5°C
2	>38.5°C – ≤ 39.0°C
3	>39.0°C

- **CCI** [REDACTED]. Severe ‘worst’ pain is defined as HZ-associated pain rated as 3 or greater on the “worst pain” question on the Zoster Brief Pain Inventory (ZBPI) questionnaire (see Sections 6.4.1 and 4.5.2.1 of the protocol). **CCI** [REDACTED]. The cases without severe “worst” pain (score ≥ 3) were considered as non-event case.
- **CCI** [REDACTED]

CCI

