10.1.2.3. Daily recording of solicited adverse events

10.1.2.3.1. Studies with paper diaries

For studies using paper diaries which have questions in the CRF indicating the presence or absence of solicited AEs, the following rules are applicable.

Denominators for the summary of local (or general) solicited AEs will be calculated using the number of subjects who respond “Yes” or “No” to the question concerning the occurrence of local (or general) AEs.

When a specific solicited AE is marked as having not occurred following a specific vaccination (i.e. SDTM CE.CEOCCUR=N for the specified post-vaccination period for the AE in question), all daily measurements will be imputed as Grade 0.

When a specific solicited AE is marked as having occurred following a specific vaccination (i.e. SDTM CE.CEOCCUR=Y for the specified post-vaccination period for the AE in question), any missing daily recordings will be given imputed values to allow them to contribute to the ‘Any’ rows but not to specific grade rows of the solicited AE summary tables.

When the occurrence of a specific solicited AE is not present (i.e. SDTM CE.CEOCCUR is neither Y nor N for the specified post-vaccination period for the symptom in question) but the group of solicited AE (local or general) is marked as having occurred (i.e. SDTM CE.CEOCCUR=Y), all missing daily recordings will be given imputed values to allow them to contribute to the ‘Any’ rows but not to specific grade rows of the solicited AE summary tables.

The following table shows how subjects contribute to each category for a specific solicited AE over the Day X to Day Y post-vaccination period:

Solicited adverse event category	Subjects included in the calculation of the numerator
Any	All subjects with at least one occurrence of the adverse event at grade 1, grade 2, or grade 3 between Day X and Day Y or with the adverse event marked as present and at least one missing daily recording between Day X and Day Y
At least grade 1	All subjects with at least one occurrence of the adverse event at grade 1, grade 2, or grade 3 between Day X and Day Y
At least grade 2	All subjects with at least one occurrence of the adverse event at grade 2 or grade 3 between Day X and Day Y
At least grade 3	All subjects with at least one occurrence of the adverse event at grade 3 between Day X and Day Y

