10.2. TFL TOC

The TFL Table Of Content (TOC) which itemizes the planned list of TFL and their associated lay-out is developed as a separate document.

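### The tables of medically attended visits are worded per AE, at odds with the SAP's subject-based rules; taken literally, the comparison between arms would depend on how many AEs each arm reports

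*Protocol*

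**What the plan says.** Protocol section 11.10 has two sentences on medically attended visits. For solicited AEs: "The proportion of solicited AEs resulting in a medically attended visit will be tabulated". For unsolicited AEs, at the end of the bullet on grade 3 and related events: "The proportion of AEs resulting in a medically attended visit will also be tabulated". SAP section 5.5.1 carries both over unchanged. Neither names a denominator other than AEs, and neither mentions an interval.

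The main AE tables in the same list are worded differently, for example: "The proportion of subjects reporting each individual solicited local and general AE during the solicited 7-day-follow-up period will be tabulated with exact 95% CI". One further bullet counts doses. So the list does distinguish between units.

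The exception is fever. After the table of the proportion of subjects by temperature, similar tabulations are planned "for any fever with a causal relationship to vaccination and for any fever resulting in a medically attended visit". In the readable text this is the only medically attended output tied to a per-subject table. Some safety bullets after these lists are blacked out.

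Two general SAP rules bear on the denominator:

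- Section 10.1.2.3.1: "Denominators for the summary of local (or general) solicited AEs will be calculated using the number of subjects who respond" yes or no to the occurrence question.
- Section 9.1.4, for a list that includes solicited and unsolicited AEs: "all vaccinated subjects will be considered and subjects who did not report an event will be considered as subjects without an event".

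Medical attention is recorded at event level (protocol section 9.3.3.4): "For each solicited and unsolicited AE/SAE the subject experiences". The SAP does not contain the table shells; under section 10.2 the list of tables and its "associated lay-out is developed as a separate document".

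**The concern.** A table of medically attended AEs is normally read as showing how many vaccinated subjects had a reaction or illness that led them to seek care. A proportion of AEs answers a different question: once an AE was reported, how often was it attended? Its denominator, the number of AEs, arises after randomisation and may itself be changed by the vaccine. Randomisation therefore does not protect the comparison of that proportion between arms.

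The comparison here is an adjuvanted vaccine against reconstituted sucrose. More AEs in the HZ/su arm is a reasonable expectation, although the documents give no counts. If the extra AEs were mostly unattended, they would enlarge the HZ/su denominator without adding to its numerator, and the table would understate any excess of attended events. What is at stake is how this part of the safety profile is read. No test or decision rule depends on it.

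**Working it through.** **A figure to reproduce.** The documents give no number of AEs or of attended visits, so there is no stated figure on this point. The only document figure used below is 713 subjects per group (protocol section 11.4). It reproduces: 10 cases / [2 × (0.0055 + 0.00275)] = 606 per group, and 606 / 0.85 = 712.9, rounded up to 713.

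**Formula.** Let m1 and m0 be the attended AEs, and a1 and a0 all AEs, in HZ/su and placebo. Let N be the common group size, and assume at most one attended AE per subject.

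- Per-subject ratio: (m1/N) / (m0/N) = m1/m0 = R.
- Per-AE ratio: (m1/a1) / (m0/a0) = (m1/m0) / (a1/a0) = R/k, with k = a1/a0.

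The two agree only at k = 1. For R > 1, the excess is attenuated when 1 < k < R, disappears at k = R and reverses when k > R. With equal risk (R = 1) the per-AE ratio is 1/k, for example 0.50 at k = 2. If k < 1, the distortion runs the other way.

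**Range.** Both R and k are assumptions. Entries are the per-AE ratio R/k.

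| True per-subject ratio R | k = 1 | k = 1.5 | k = 2 | k = 3 | k = 4 | k = 6 |
|---|---|---|---|---|---|---|
| 1.5 | 1.50 | 1.00 | 0.75 | 0.50 | 0.38 | 0.25 |
| 2 | 2.00 | 1.33 | 1.00 | 0.67 | 0.50 | 0.33 |
| 3 | 3.00 | 2.00 | 1.50 | 1.00 | 0.75 | 0.50 |

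**One worked case** (assumed counts, except for 713): placebo has 10 attended AEs among 500; HZ/su has 20 among 2000, so R = 2 and k = 4.

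- Per AE: 20/2000 = 1.00% against 10/500 = 2.00%, which looks like a halving.
- Per subject: 20/713 = 2.81% (exact 95% CI 1.72 to 4.30) against 10/713 = 1.40% (0.67 to 2.56), a doubling.

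The per-subject result does not change with k. With the same attended counts and k = 1.5, the per-AE figures are 20/750 = 2.67% against 2.00%: the excess is smaller but still visible.

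**Do the general SAP rules settle the denominator?** Section 10.1.2.3.1 is subject-based, but it covers daily diary recordings of solicited AEs. Its category table covers any, and at least grade 1, 2 or 3; it does not mention medical attendance or unsolicited AEs. Section 9.1.4 says which subjects are considered and how non-reporters are handled; it does not redefine a proportion expressed in AEs. Sections 10.1.3.6 and 10.1.3.7 give rules for counting AE occurrences, so an event count is a workable reading. The two readings are left side by side.

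**The case against.** The strongest case against is that this is shorthand, not a choice of AEs as denominator. The unsolicited sentence closes a bullet that begins by calling for the same tabulation as the preceding proportion-of-subjects table. Attended fever follows a per-subject table. The general SAP rules are subject-based, and the shells, which were not available for this review, may already use subjects. That stands as far as it goes: the AE denominator cannot be treated as fixed. It does not make the sentences correct, because none of those rules names medically attended visits outside fever.

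A reader might infer that the plan is biased towards making HZ/su look safer, or that a true excess will appear as a reduction. The documents do not support either. They give no AE counts by arm and no share of AEs that were attended. Reversal needs k > R; below that the excess is reduced or hidden, not reversed. Nor do the documents give a figure to show that k would materially exceed 1 for unsolicited AEs over 30 days.

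The reach is also limited. Secondary analyses are descriptive, and no between-arm ratio or test of attended AEs is planned; the ratio above is the one a reader would form. Medical attendance is not among the readable secondary endpoints. Severity is covered per subject by the any-AE and grade 3 tables, and SAEs and AEs leading to withdrawal are tabulated too. All of this stands and limits the weight of the point. It does not remove the need to say what the table counts.

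**Conclusion.** The point holds as an inconsistency in the specification that should be corrected. Both documents word the attended-visit tables per AE and without an interval, while the neighbouring tables and the general SAP rules are per subject. If the shells follow the wording, the comparison between arms is R/k rather than R. If the shells use subjects, the SAP misdescribes its own table.

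The size depends wholly on k, which the documents do not give: there is no distortion at k = 1, and a true doubling would show as 1.33 at k = 1.5, 1.00 at k = 2 and 0.50 at k = 4. These values assume equal arms and at most one attended AE per subject. The claim that the plan will reverse a true excess goes further than the documents allow. The primary non-inferiority conclusion is unaffected.

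**What to change.** In SAP section 5.5.1, and in protocol section 11.10 if the protocol is amended, replace both sentences with: the number and percentage of subjects with at least one solicited (respectively unsolicited) AE resulting in a medically attended visit will be tabulated with exact 95% CI, after each dose and overall. Use the same subject denominators as the corresponding solicited and unsolicited AE tables. If a per-AE proportion is wanted, keep it as a supplement with its numerator and denominator shown. Check that the table shells match.

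The cost is two sentences in the SAP, two more in the protocol if it is amended, and a check of the shells. No new data are needed, because attendance is already recorded for each AE.
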